This Statistical Analysis Plan (SAP) supplements the main study protocol and prespecifies analyses for all primary, secondary, and exploratory outcomes. This amended version was finalized prior to database lock and unblinding, and follows contemporary guidance for SAP content in clinical trials (Gamble *et al.*, 2017).

Signature Page

We, the undersigned, approve and will adhere to the Statistical Analysis Plan detailed herein:

SAP authors

| Name | Title | Role | Signature | Date |
|--|-------|--|--|---------------------|
| [name] ¹ | PhD | Sponsor- investigator; SAP co-author |  | 21 February 2026 |
| [name] ² | PhD | SAP co-author |  | 21 February 2026 |

¹Faculty of Health, University of the Faroe Islands, Tórshavn, Faroe Islands

²Department of Biomedical Sciences, University of Copenhagen, Copenhagen, Denmark

Section 2: Introduction

7. Background and Rationale (adapted from the published protocol)

Detailed background and rationale are presented in the published protocol (Sjúrðarson *et al.*, 2025). In brief, statins are first-line therapy for dyslipidaemia but have been hypothesized to attenuate exercise-induced improvements in skeletal-muscle mitochondrial content and function as well as cardiorespiratory fitness (Mikus *et al.*, 2013). This trial is designed to quantify the exercise × statin interaction on mitochondrial function and related physiological and clinical markers in middle-aged adults with dyslipidaemia, using citrate synthase (CS) maximal activity as a validated biomarker of mitochondrial content/oxidative capacity and peak oxygen uptake (VO_{2peak}) as a complementary integrated marker of whole-body fitness. The central scientific question is whether concomitant high-dose atorvastatin attenuates adaptations normally observed with supervised high-intensity interval training.

8. Objectives

Overall objective. To estimate the individual and combined effects of 12 weeks of atorvastatin and supervised exercise training on physiological, biochemical, and patient-reported outcomes in adults with dyslipidaemia.

Primary objective.

To evaluate the effect of 12 weeks of atorvastatin, exercise training, and their combination on skeletal-muscle CS maximal activity across all four intervention groups.

The main mechanistic contrast of interest is Exercise + Placebo vs Exercise + Atorvastatin, testing whether atorvastatin blunts training-induced mitochondrial adaptations.

Additional pre-specified pairwise comparisons among the four groups will be analyzed to fully characterize exercise, drug, and combined effects (see Section 12).

Key secondary objective.

To evaluate changes in VO_{2peak} ($\text{mL}\cdot\text{kg}^{-1}\cdot\text{min}^{-1}$) across the four groups, with the same principal contrast (Exercise + Placebo vs Exercise + Atorvastatin), testing whether atorvastatin blunts training-induced adaptations in VO_{2peak} .

For details on outcome selection and rationale, see the published protocol.

Section 3: Study Methods

9. Trial design

This investigator-initiated, randomized, double-blinded (medication) and placebo-controlled trial evaluates the effects of high-dose atorvastatin and supervised high-intensity interval training (HIIT), alone or combined, over 12 weeks in adults with dyslipidaemia. Participants are allocated to one of four parallel arms:

1. Exercise + Placebo
2. Exercise + Atorvastatin
3. No Exercise + Atorvastatin
4. No Exercise + Placebo

Medication allocation is double-blinded (participants and investigators). Exercise allocation cannot be blinded to participants or trainers; however, outcome assessors and laboratory personnel will remain blinded to medication allocation, and data analysts will remain blinded to both medication and exercise allocation until database lock.

Interventions

- **Wash-out:** 4-week discontinuation of lipid-lowering therapy before baseline (week 0).
- **Medication:** Atorvastatin 40 mg (Week 1-2), then 80 mg daily; matching placebo in placebo arms.
- **Exercise:** Supervised high-intensity interval training (HIIT) three times per week, performed at or above 90 % of maximal aerobic power (MAP), with intensity monitored using power output (wattage), heart rate (HR), and ratings of perceived exertion (RPE).
- **Non-exercise arms:** Maintain habitual physical activity.

Study visits:

V0 = Screening, V1 = Baseline (all measurements completed before randomization), Week 6 = mid-intervention blood samples and questionnaires, V2 = Post-intervention (12 weeks).

10. Randomization

Randomization uses a computer-generated list prepared by an independent statistician. Allocation is performed by a non-involved colleague after completion of baseline assessments. Participants are randomized in a 60:40 exercise:non-exercise ratio to achieve approximately:

| Group | n |
|-----------------------------------|----------|
| Exercise + Placebo | 36 |
| Exercise + Atorvastatin | 36 |
| No Exercise + Atorvastatin | 24 |
| No Exercise + Placebo | 24 |

Randomization is stratified by:

1. Sex (male/female)
2. Prior active statin treatment (yes/no)

Block sizes are concealed from investigators. Randomization codes are securely stored and revealed only after database lock.

11. Sample size calculations

Sample-size calculations were prespecified for the primary mechanistic contrast (Exercise + Placebo vs Exercise + Atorvastatin) for the primary endpoint (Δ CS) and the key secondary endpoint (Δ VO_{2peak}).

Power calculations (as prespecified in the published protocol) used prior training data (Sjúrðarson *et al.*, 2022a, 2022b): mean $\Delta\text{CS} \approx 25 \mu\text{mol}\cdot\text{g}^{-1}\cdot\text{min}^{-1}$, SD $\approx 18 \mu\text{mol}\cdot\text{g}^{-1}\cdot\text{min}^{-1}$, and a target between-group difference of $17 \mu\text{mol}\cdot\text{g}^{-1}\cdot\text{min}^{-1}$, consistent with attenuation magnitudes reported previously (Mikus *et al.*, 2013). For $\text{VO}_{2\text{peak}}$, we assumed $\Delta \approx 3.6 \pm 3.3 \text{ mL}\cdot\text{kg}^{-1}\cdot\text{min}^{-1}$ and targeted a $3.0 \text{ mL}\cdot\text{kg}^{-1}\cdot\text{min}^{-1}$ between-group difference.

Final enrolled sample size.

A total of $N = 120$ participants were randomized (36 per exercise arm; 24 per non-exercise arm). The primary mechanistic comparison—Exercise + Placebo vs Exercise + Atorvastatin—is effectively a two-group contrast, and power calculations were therefore based on the two exercise groups.

Using the effect-size assumptions prespecified in the published protocol, the achieved sample provides:

- **Citrate synthase (CS) activity:**
 - With full enrollment ($n = 36$ per group), power is approximately 97–98% to detect a $17 \mu\text{mol}\cdot\text{g}^{-1}\cdot\text{min}^{-1}$ difference (SD ≈ 18).
 - With 10% attrition (≈ 33 per group), power remains high at ≈ 94 –95%.

- **$\text{VO}_{2\text{peak}}$:**
 - With full enrollment ($n = 36$ per group), power is approximately 96–97% to detect a $3.0 \text{ mL}\cdot\text{kg}^{-1}\cdot\text{min}^{-1}$ difference (SD ≈ 3.3).
 - With 10% attrition (≈ 33 per group), power remains ≈ 93 –95%.

Power calculations were performed in G*Power (version 3.1.9.7) using a two-sample, two-sided t-test with $\alpha = 0.05$, assuming equal group sizes for the exercise arms. Power calculations are based on a two-sample t-test approximation for the primary exercise-arm contrast; the primary analysis will use a constrained mixed model, which is expected to provide similar or greater efficiency under the repeated-measures structure.

Interpretation note (pre-specified).

Because (i) a clinically meaningful CS difference is not firmly established and (ii) assay units/conditions vary across studies, true between-group differences smaller than $17 \mu\text{mol}\cdot\text{g}^{-1}\cdot\text{min}^{-1}$ may still be clinically relevant.

For $\text{VO}_{2\text{peak}}$, relatively small differences may also be clinically meaningful. While meta-analytic evidence indicates that each 1-MET ($\approx 3.5 \text{ mL}\cdot\text{kg}^{-1}\cdot\text{min}^{-1}$) higher cardiorespiratory fitness is associated with substantially lower all-cause and cardiovascular mortality risk (Myers *et al.*, 2002; Kodama *et al.*, 2009), prospective cohorts with directly measured $\text{VO}_{2\text{peak}}/\text{VO}_{2\text{max}}$ also demonstrate prognostic gradients per $\sim 1 \text{ mL}\cdot\text{kg}^{-1}\cdot\text{min}^{-1}$, implying that differences on the order of $\sim 2 \text{ mL}\cdot\text{kg}^{-1}\cdot\text{min}^{-1}$ are clinically meaningful (Keteyian *et al.*, 2008; Laukkanen *et al.*, 2016; Khan *et al.*, 2018; Tari *et al.*, 2024). Accordingly, a between-group difference of $\sim 2.0 \text{ mL}\cdot\text{kg}^{-1}\cdot\text{min}^{-1}$ (≈ 0.6 MET) can be considered a clinically relevant difference in $\text{VO}_{2\text{peak}}$.

With 120 randomized participants, the study has approximately 80% power to detect between-group differences of $\sim 12 \mu\text{mol}\cdot\text{g}^{-1}\cdot\text{min}^{-1}$ in CS activity and $\sim 2.1 \text{ mL}\cdot\text{kg}^{-1}\cdot\text{min}^{-1}$ in $\text{VO}_{2\text{peak}}$.

12. Framework

Analyses will follow a superiority framework. For the primary endpoint (change in CS activity), all four groups will be compared with each other (six pre-specified pairwise contrasts). Multiplicity across the six tests will be controlled using the Holm–Šidák procedure, maintaining a familywise two-sided $\alpha = 0.05$. Superiority will be claimed only for contrasts meeting this adjusted criterion.

All secondary and exploratory outcomes, including $\text{VO}_{2\text{peak}}$, will be analyzed using the same general model framework, with emphasis on effect estimates and 95% confidence intervals; p-values will be reported without multiplicity adjustment and should not be used to infer definitive treatment effects.

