12.1 Statistical Hypotheses

The primary mechanistic hypothesis is that supervised exercise training increases skeletal-muscle CS activity and that concomitant high-dose atorvastatin attenuates this response.

The key secondary hypothesis is that concomitant atorvastatin treatment attenuates training-induced improvements in cardiorespiratory fitness, assessed as the between-group difference in change in VO_{2peak} between Exercise + Placebo and Exercise + Atorvastatin.

For the primary endpoint (ΔCS), six pre-specified pairwise contrasts will be evaluated to characterize exercise, statin, and combined effects:

| No. | Comparison | Scientific question |
|-----|--|--|
| 1 | Exercise + Placebo > Exercise + Atorvastatin | Does atorvastatin blunt exercise-induced mitochondrial gains? (Primary contrast) |
| 2 | Exercise + Placebo > No Exercise + Atorvastatin | Benefit of exercise alone vs. drug alone |
| 3 | Exercise + Placebo > No Exercise + Placebo | Absolute effect of exercise training |
| 4 | Exercise + Atorvastatin > No Exercise + Atorvastatin | Can exercise mitigate potential statin-related attenuation? |
| 5 | Exercise + Atorvastatin > No Exercise + Placebo | Combined treatment vs. no intervention |
| 6 | No Exercise + Placebo > No Exercise + Atorvastatin | Do statins alone affect mitochondrial function? |

Contrasts are listed in the hypothesized direction for interpretation; all tests will be two-sided.

13. Statistical interim analyses and stopping guidance

No interim analyses for efficacy are planned. No early stopping guidelines were specified.

14. Timing of final analysis

Data collection is considered complete after the last participant's last visit. Analyses will begin only after:

1. all data have been entered and cleaned,
2. all queries have been resolved, and
3. The randomization code has been formally unblinded following database lock.

No unblinded interim looks are permitted before database lock.

15. Timing of outcome assessments

Primary and secondary outcomes are measured at V1 (baseline) and V2 (12 weeks). Blood samples and questionnaire data are collected at V1, week 6, and V2.

Section 4: Statistical principles

16–18. Confidence Intervals, P-values, and Multiplicity

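### The SAP says the trial is designed to quantify the exercise × statin interaction, but no planned contrast estimates it, and the atorvastatin effect among exercisers is read as blunting of training.

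*SAP*

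**What the plan says.** Section 2, item 7 gives the design aim: "This trial is designed to quantify the exercise × statin interaction on mitochondrial function".

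Item 8 moves to a two-arm comparison and gives it the same meaning: "The main mechanistic contrast of interest is Exercise + Placebo vs Exercise + Atorvastatin, testing whether atorvastatin blunts training-induced mitochondrial adaptations". The key secondary objective for VO2peak follows suit, "with the same principal contrast (Exercise + Placebo vs Exercise + Atorvastatin), testing whether atorvastatin blunts training-induced adaptations". Section 11 says that the primary comparison "is effectively a two-group contrast, and power calculations were therefore based on the two exercise groups".

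Section 12 fixes six pairwise comparisons of the four arms for CS, with Holm–Šidák control. In the table in Section 12.1, contrast 1 carries the question "Does atorvastatin blunt exercise-induced mitochondrial gains". Contrast 6 compares the two non-exercise arms, with placebo listed above atorvastatin, and the note under the table says that contrasts are written in the hypothesised direction. Attenuation of VO2peak is "assessed as the between-group difference in change in VO_{2peak} between Exercise + Placebo and Exercise + Atorvastatin".

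The model in Section 27 has a four-level group × time term. The only other interactions named anywhere are the exploratory ones with genotype (29.3) and sex (29.4).

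**The concern.** Blunting of the training response means that training adds less under atorvastatin than under placebo. That is a difference of differences and involves all four arms. Contrast 1 involves only the two exercise arms, so it cannot separate two explanations: atorvastatin weakens the response to training, or atorvastatin lowers CS whether or not people train.

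The SAP nowhere assumes that atorvastatin has no effect without training. By its own note, contrast 6 is written in the direction of a loss. Under that hypothesis contrast 1 contains the loss without training and overstates blunting.

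There is also a risk in the reading of results. If contrast 1 is significant and contrast 6 is not, the pair looks like evidence of blunting, but a difference in significance does not test the difference between the two effects.

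**Working it through.** **Inputs.** From Sections 10 and 11: arms of 36, 36, 24 and 24; SD of change 18 for CS and 3.3 for VO2peak; target differences 17 and 3.0; two-sided α = 0.05. The SAP gives no SD of change for the non-exercise arms, so I assume the same SD, two thirds of it, or half of it. As in Section 11, the calculation uses change scores; the constrained model may be somewhat more precise.

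**The plan's own figure.** Contrast 1 for CS: SE = 18·√(2/36) = 4.24, and the noncentral t gives 97.7% power for 17 (SAP: 97–98%). For VO2peak, SE = 3.3·√(2/36) = 0.78, with 96.7% power for 3.0 (SAP: 96–97%). Both reproduce, unadjusted for multiplicity.

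**Is the interaction among the six contrasts?** Write EP, EA, NP and NA for the mean changes in Exercise + Placebo, Exercise + Atorvastatin, No Exercise + Placebo and No Exercise + Atorvastatin.

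- Interaction = (EP − NP) − (EA − NA), with four non-zero coefficients.
- Each planned contrast has two non-zero coefficients, so none is proportional to it.
- Interaction = (EP − EA) − (NP − NA), that is, contrast 1 minus contrast 6. It also equals contrast 3 minus contrast 4. Neither difference is planned.

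Hence contrast 1 equals the interaction only if NP − NA = 0.

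**Size of the overstatement.** Hold contrast 1 at 17 and let the loss without training be L, so the interaction is 17 − L.

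| L (assumed) | Interaction | Overstatement |
|---|---|---|
| 3 | 14 | 17/14 − 1 = 21% |
| 5 | 12 | 17/12 − 1 = 42% |
| 8 | 9 | 17/9 − 1 = 89% |

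**Precision of the interaction.** With s the non-exercise SD, SE = √(2·18²/36 + 2·s²/24) for CS, and the same with 3.3 for VO2peak. Degrees of freedom are Satterthwaite.

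| Outcome | s (assumed) | SE | 95% CI half-width | Power for target |
|---|---|---|---|---|
| CS | 18 | 6.71 | 13.3 | 71% |
| CS | 12 | 5.48 | 10.9 | 87% |
| CS | 9 | 4.97 | 9.9 | 92% |
| VO2peak | 3.3 | 1.23 | 2.4 | 68% |
| VO2peak | 2.2 | 1.00 | 2.0 | 84% |
| VO2peak | 1.65 | 0.91 | 1.8 | 90% |

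The half-widths for contrast 1 are 8.5 (CS) and 1.6 (VO2peak).

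**How often the misleading pattern arises.** A simulation of 100,000 trials per cell set the mean changes in CS to EP = 25, EA = 25 − d, NP = 0 and NA = −d. Atorvastatin then lowers CS by d with or without training, and the true interaction is zero. Holm–Šidák was applied over the six tests. The table gives the percentage of trials with contrast 1 significant and contrast 6 not.

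| Non-exercise SD and variance used in the tests | d = 3 | 5 | 8 | 12 | 17 |
|---|---|---|---|---|---|
| 18 | 5.7 | 11.8 | 24.1 | 28.5 | 12.5 |
| 12, separate by arm | 5.4 | 10.0 | 13.2 | 5.7 | 0.3 |
| 12, pooled over arms | 10.0 | 18.3 | 28.2 | 17.1 | 1.8 |
| 9, separate by arm | 5.0 | 7.5 | 5.2 | 0.4 | 0.0 |
| 9, pooled over arms | 12.4 | 21.8 | 28.8 | 8.9 | 0.2 |

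At SD 18, contrast 6 is itself significant in 57% of trials at d = 12 and 87% at d = 17, so a large effect without training would usually be seen.

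**The case against.** The strongest defence is that the working estimand is consistent. The interaction is named once, in a background item adapted from the published protocol, while the objectives, the power section and the hypotheses all use the two exercise arms. Rewording item 7 would remove the literal contradiction. That is true, but it would leave contrast 1 labelled as a test of blunting, which it is not.

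Little information is lost. Changes and differences are reported with 95% CIs, contrasts 1 and 6 use different arms, and a reader can subtract one from the other and approximate the interval. Contrast 6 is also a multiplicity-controlled look at the effect without training. This stands and limits the severity. Still, readers should not have to reconstruct the quantity that the trial says it was designed to quantify, and a non-significant contrast 6 does not show that the effect is zero.

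Contrast 6 is also worded as an open question and tested two-sided, and the SAP gives no size for a loss without training. The percentages above therefore rest on assumed values.

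The simulated rates are not error rates of any SAP procedure: contrast 1's null is false in every cell, and the SAP gives no rule that infers blunting from the pair of results. The reverse pattern (contrast 6 significant, contrast 1 not) also occurs, in about 27% of trials at SD 12 and 42% at SD 9 for d = 8 with separate variances. That pattern would mislead in the other direction, which again argues for estimating the interaction directly.

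Finally, Section 27 names one covariance pattern and no variance by arm. With a pooled variance and non-exercise SD 12, the pooled SD is √((70·18² + 46·12²)/116) = 15.9, and the CS half-widths become about 7.4 for contrast 1 and 11.7 for the interaction. The figures move, but the conclusion does not.

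For VO2peak the stakes are lower, because Section 12 says that its p-values "should not be used to infer definitive treatment effects".

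**Conclusion.** The concern holds and should be fixed. The stated aim is an interaction, no planned contrast estimates it, and the conclusion attached to contrast 1 needs an assumption that the SAP does not make and that its own contrast 6 runs against. The algebra needs no numerical assumption. The size does: an overstatement of 21% to 89% for losses without training of 3 to 8, and a misleading pair of results in up to about 29% of trials when the true interaction is zero, depending on the effect, the non-exercise SD and the variance model.

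Contrast 1 remains a valid test of its own null, is consistently named as primary, and has the power claimed for it. That power does not carry over to the interaction. With a common SD the interaction's variance is 2.5 times as large (6.71²/4.24²), and its power for 17 is about 71%.

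**What to change.** - In Sections 12.1 and 27, add as a supportive estimate with 95% CI, for CS and VO2peak: (Ex+Placebo − NoEx+Placebo) − (Ex+Atorvastatin − NoEx+Atorvastatin) in change from V1 to V2. Take it from the same constrained model and keep it outside the Holm–Šidák family.
- Keep contrast 1 as the primary, powered contrast. In items 8 and 12.1, describe it as the effect of atorvastatin in people who train, and make the matching change to the VO2peak hypothesis.
- State that any claim about blunting or attenuation is reported together with the interaction estimate and its CI, without a significance gate.
- State that the interaction is less precise than contrast 1, and that its precision depends on the non-exercise SD, which Section 11 does not give.
- If the database is already locked when this is added, report the interaction as post hoc.

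The cost is one extra linear contrast from a model already planned, plus wording. No new data are needed, and neither the multiplicity scheme nor the power of contrast 1 changes. The price is the wider interval shown above, which may leave the blunting question open even if contrast 1 is clear.

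### Section 11 states CS power for the primary contrast at an unadjusted 0.05, but Section 12 decides that contrast under six-test Holm–Šidák, so about 80% at 12 units is not its power under the plan's rule

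*SAP*

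**What the plan says.** Section 11 bases its power statements on the two exercise arms: "Power calculations were performed in G*Power (version 3.1.9.7) using a two-sample, two-sided t-test with" α = 0.05. On that footing it gives three CS figures.

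- "With full enrollment ($n = 36$ per group), power is approximately 97–98% to detect a" 17-unit difference, with SD about 18.
- "With 10% attrition (≈ 33 per group), power remains high at" about 94–95%, for the same difference.
- In the sentence that closes the interpretation note: "With 120 randomized participants, the study has approximately 80% power to detect between-group differences of" about 12 units in CS and about 2.1 in VO2peak.

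It adds that the constrained mixed model, "which is expected to provide similar or greater efficiency under the repeated-measures structure", will be the actual analysis. Multiplicity is not mentioned anywhere in Section 11.

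Section 12 places all six pairwise CS contrasts under Holm–Šidák at a familywise two-sided 0.05 and adds: "Superiority will be claimed only for contrasts meeting this adjusted criterion". Sections 16–18 repeat the rule. Section 12.1 marks contrast 1 ("Does atorvastatin blunt exercise-induced mitochondrial gains") as the primary contrast. No section tests it first, exempts it from the adjustment or gives it its own alpha. For VO2peak, Section 12 says that "p-values will be reported without multiplicity adjustment and should not be used to infer definitive treatment effects".

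**The concern.** The power is computed for one test at 0.05, but that test is decided as one of six. Under Holm–Šidák, contrast 1 is judged at 0.05 only when the other five contrasts have all been rejected with smaller p-values. One of those five is the effect of atorvastatin without exercise (contrast 6).

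The 12-unit sentence matters because it ends a pre-specified note saying that CS differences below 17 may still be relevant. If contrast 1 is not significant, a reader could use that sentence to argue that a true difference of 12 would have been found about four times in five. If the real chance is nearer two in three, the null result is weaker evidence against a 12-unit attenuation than the plan suggests.

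**Working it through.** **Inputs.** From Section 11: SD of change in CS 18, mean training gain 25, 36 per exercise arm (33 after 10% attrition), two-sided 0.05, SD 3.3 for VO2peak. From Section 10: 24 per non-exercise arm (22 after 10% attrition: 24 × 0.9 = 21.6). From Section 12: six contrasts under Holm–Šidák. The SAP does not give expected mean changes in the non-exercise arms or the baseline–follow-up correlation, so both are varied below as assumptions.

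**Step 1: reproduce the plan's figures at unadjusted 0.05.** Noncentral t with noncentrality d / (SD·√(2/n)) and 2n − 2 degrees of freedom.

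- CS, d = 12, n = 36: 12 / (18·√(2/36)) = 2.83, power 79.7%. The stated 80% reproduces.
- CS, d = 17, n = 36: noncentrality 4.01, power 97.7%. The stated 97–98% reproduces.
- CS, d = 17, n = 33: noncentrality 3.84, power 96.5%. The stated 94–95% does not reproduce; it would correspond to 29–30 per arm.
- VO2peak, d = 2.1, n = 36: 2.1 / (3.3·√(2/36)) = 2.70, power 75.9%. The stated 80% does not reproduce; 80% needs 2.21. As a cross-check, 12/18 = 0.667 equals 2.2/3.3, whereas 2.1/3.3 = 0.636.

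**Step 2: bounds for contrast 1 under Holm–Šidák.** The step levels are 1 − 0.95^(1/k) for k = 6 to 1: 0.00851, 0.01021, 0.01274, 0.01695, 0.02532, 0.05. A p-value at or below 0.00851 always passes and one above 0.05 never does. Power at these two levels therefore bounds the true value whatever the other arms do.

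| Difference | n per exercise arm | Floor (0.00851) | Ceiling (0.05) |
|---|---|---|---|
| 12 | 36 | 55.1% | 79.7% |
| 12 | 33 | 50.2% | 76.0% |
| 17 | 36 | 89.9% | 97.7% |
| 17 | 33 | 86.5% | 96.5% |

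At the floor level, 80% power needs a difference of 15.1 (36 per arm) or 15.8 (33 per arm).

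**Step 3: within the bounds.** The full six-contrast step-down was simulated (200,000 runs, SD 18, arms 36/36/24/24 or 33/33/22/22). Mean changes were 25 for Exercise + Placebo, 25 − d for Exercise + Atorvastatin and, as an assumption, 0 in both non-exercise arms. Ranges cover pooled-variance and pairwise t-tests.

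| Quantity | 36 per exercise arm | 33 per exercise arm |
|---|---|---|
| Power at d = 12 | 67–68% | 62–63% |
| Power at d = 17 | about 94% | about 91% |
| d for 80% power | 13.7–13.9 | 14.4–14.6 |

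Other assumed means, d = 12: if atorvastatin without exercise lowers CS by 5 to 12, power is about 69–74% (36 per arm) or 64–69% (33). If both non-exercise arms rise by 5, it is about 64% or 58%.

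**Step 4: credit for baseline adjustment.** With equal V1 and V2 variances (assumption), adjusting for baseline reduces the SD from 18 to 18·√((1 + r)/2), where r is the baseline–follow-up correlation. The ranges run over a non-exercise atorvastatin effect of 0 to −12, with d = 12 and the full step-down.

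| r | 36 per exercise arm | 33 per exercise arm |
|---|---|---|
| 0.5 | 83–88% | 79–84% |
| 0.75 | 76–81% | 71–76% |
| 0.9 | 71–76% | 66–72% |

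With no atorvastatin effect at rest and 36 per arm, 80% is recovered when r is about 0.6 or lower.

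**The case against.** The strongest reply is that the decision rule is applied to the constrained mixed model of Section 27, not to t-tests on change scores. With baseline adjustment, adjusted power at 12 units and 36 per arm runs from 71% to 88% over the values tried, and 80% lies inside that range. This stands as far as it goes: a shortfall under the actual model is not proven. Nor is 80%. It depends on a correlation and on arm means that the SAP does not state, and the SAP itself claims no more than similar or greater efficiency. With similar efficiency the gap remains.

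It is also fair to say that Section 11 discloses its unadjusted 0.05, so the CS sentence is correct on its stated basis. But that sentence presents the figure as the power of the study, and nothing tells the reader that the contrast is decided by a stricter rule.

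The assumption of no change in the non-exercise arms can be challenged, because Section 12.1 lists contrast 6 in the direction of a statin effect. Allowing for one raises t-test power at 36 per arm only to about 69–74%. The 55% floor is indeed remote; it is a bound, not an expectation.

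Finally, the two side figures are small. The 33-per-arm CS figure errs on the cautious side. The VO2peak figure is marked as approximate, its p-values are not meant for definitive inference, and baseline adjustment could lift it as well. Both still disagree with the inputs given beside them.

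**Conclusion.** The concern holds. Section 11's CS power is not the power of contrast 1 under the rule in Sections 12 and 16–18. On the SAP's own t-test basis, about 80% at 12 units is the most that contrast can have with 36 per arm. About two in three is the working value if training adds 25 and the non-exercise arms do not change on average. Whether the mixed model restores 80% cannot be settled from the document.

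The VO2peak and 33-per-arm CS discrepancies need no assumption about other arms and have nothing to do with multiplicity.

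The reach is limited. Power at the 17-unit design target is at least 90% at full enrolment and at least 86% at 33 per arm. Familywise error, estimates, confidence intervals, sample size, model and tests are all unaffected. What is affected is how a non-significant primary contrast would be read, so this should be corrected.

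**What to change.** Keep the testing rule and reword Section 11.

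1. Replace the 12-unit sentence, for example: *At an unadjusted two-sided 0.05 (two-sample t-test, 36 per exercise arm), power is about 80% for a difference of 12 in CS (SD 18) and 2.2 in VO2peak (SD 3.3). Under the six-test Holm–Šidák rule that decides the CS contrast, power at 12 is about 68% and 80% is reached at about 14, assuming a training gain of 25 and no mean change in the non-exercise arms.* The sponsor may substitute its own adjusted calculation if the assumptions are shown.
2. In the 17-unit CS bullets, say that 97–98% is at unadjusted 0.05 and correct the 33-per-arm figure from 94–95% to about 96.5%. Add the adjusted values: about 94% (floor 90%) at 36 per arm and about 91% (floor 86%) at 33 per arm.
3. If the mixed model is relied on to recover power at 12 units, state the assumed baseline–follow-up correlation and non-exercise arm means, and show the calculation.

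The cost is wording in one section before database lock. The CS figures will look less favourable, and the adjusted ones rest on assumed means that have to be disclosed.

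### SAP Section 11 claims about 80% power for a VO2peak difference of ~2.1 mL/kg/min; its own inputs give 76% there and reach 80% at about 2.2

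*SAP*

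**What the plan says.** Section 11 ties all its power figures to one comparison, Exercise + Placebo against Exercise + Atorvastatin: "power calculations were therefore based on the two exercise groups". The enrolled numbers are given as 120 who "participants were randomized (36 per exercise arm; 24 per non-exercise arm"). The method is a two-sided two-sample t-test in G*Power at alpha 0.05, "assuming equal group sizes for the exercise arms". The assumed SD of change is about 18 µmol/g/min for CS and about 3.3 mL/kg/min for VO2peak.

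The interpretation note then argues that a VO2peak difference of about 2.0 mL/kg/min "can be considered a clinically relevant difference in" VO2peak. The section's closing sentence follows at once: "With 120 randomized participants, the study has approximately 80% power to detect between-group differences of" roughly 12 in CS and roughly 2.1 in VO2peak. It gives no other SD, sample size, correlation or method for these two figures.

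**The concern.** Both detectable differences are quoted in one sentence at the same power. With the same test, alpha and group sizes, each should equal the same multiple of its SD. They do not, so at least one cannot be right.

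What is at stake is how the design is described. Because the sentence comes straight after the claim that about 2.0 mL/kg/min matters clinically, a figure of 2.1 suggests that the trial has close to 80% power for the relevant difference. A reader faced with an inconclusive VO2peak interval would use this sentence to judge what the trial could have shown.

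**Working it through.** **Inputs (all from SAP Section 11).** n = 36 per exercise arm; two-sided alpha = 0.05; SD = 18 (CS) and 3.3 (VO2peak). Section 12 applies no multiplicity adjustment to VO2peak, so 0.05 is the right alpha for it.

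**Formula.** With equal groups of size n, difference δ and SD σ, the test statistic follows a noncentral t distribution with df = 2n − 2 and noncentrality λ = (δ/σ)·√(n/2). Power = P(|T| > t crit), where t crit is the 97.5th percentile of the central t. For n = 36: df = 70, t crit = 1.994 and √(36/2) = 4.243.

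**Step 1: reproduce the plan's other full-enrolment figures.**

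| Outcome | δ | δ/σ | λ | Power | SAP states |
|---|---|---|---|---|---|
| CS | 17 | 0.944 | 4.007 | 97.7% | 97–98% |
| VO2peak | 3.0 | 0.909 | 3.857 | 96.7% | 96–97% |
| CS | 12 | 0.667 | 2.828 | 79.7% | about 80% |

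These three agree, so the method and inputs are those the plan used at 36 per arm.

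**Step 2: the disputed figure.** δ/σ = 2.1/3.3 = 0.636; λ = 0.636 × 4.243 = 2.700; power = **75.9%**, against a stated 80% or so. The normal approximation gives 77.0%.

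**Step 3: the difference that does give 80%.** At n = 36 per arm, 80% power needs δ/σ = 0.6696.

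- CS: 0.6696 × 18 = 12.05, which rounds to the stated 12.
- VO2peak: 0.6696 × 3.3 = **2.21**, which rounds to 2.2 (normal approximation 2.18, also 2.2). Power at 2.2 is 79.7%, the same as CS at 12, because 2.2/3.3 = 12/18.

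**Step 4: can another reading yield 2.1?**

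- One-sided alpha 0.05: 84.8% at 2.1.
- Pooled groups: 72 against 48 gives 92.3%; 60 against 60 gives 93.3%.
- 33 per arm (10% attrition): 72.1%.
- Rounding of the difference alone (true value 2.149): 77.8%.
- Rounding of both inputs at their favourable limits (2.149 and SD 3.25): 79.0%.
- What 80% at 2.1 would require: SD = 2.1/0.6696 = 3.14, or 40 per arm (80.3%).

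Only the double-rounding case comes near 80%, and it needs an SD other than the stated one.

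**Step 5: power at the difference the plan calls relevant.** At 2.0, power is 71.8% with 36 per arm and 67.9% with 33 per arm. With 33 per arm, 80% power is reached at 2.31.

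**The case against.** Four points can be made for the plan.

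- **Precision.** The sentence is hedged on both power and difference, and the SD is itself approximate. This limits the weight of the point but does not remove it: at the same one-decimal precision the right figure is 2.2, and the equally hedged CS figure is correct.
- **Other loose figures.** At 33 per arm the stated method gives 96.5% for CS at 17, where the plan says about 94–95%, and 95.3% for VO2peak at 3.0, at the top edge of its 93–95%. So not every figure in Section 11 is exact, and the CS one errs on the cautious side. That is fair, but those are attrition figures. The disputed sentence refers to all randomized participants, and every other full-enrolment figure reproduces.
- **Mixed-model efficiency.** The plan expects its constrained mixed model to be at least about as efficient as the t-test. Baseline adjustment scales the SD of change by √((1+ρ)/2), where ρ is the correlation between the two visits. The plan gives neither ρ nor a cross-sectional SD. If the between-person SD is assumed to be 4.5 to 7 mL/kg/min, with SD of change 3.3, power at 2.1 would be about 82% to 78%. So real power may well be nearer 80% than 76%. But the plan says its power figures rest on the t-test, and the CS figure in the same sentence contains no such gain.
- **No consequence for the analysis.** All participants are randomized, the design target was 3.0, and Section 12 reports VO2peak "with emphasis on effect estimates and 95% confidence intervals". This stands, and it is why the point is minor.

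**Conclusion.** The VO2peak figure is wrong as written. Under the plan's stated test, alpha, SD and group size, power at 2.1 mL/kg/min is 75.9%, and the difference detectable with 80% power is 2.21. The size is about 4 points of power, or 0.1 mL/kg/min, in the favourable direction. The conclusion assumes only the inputs printed in Section 11. The mismatch between 0.636 and 0.667 within the sentence shows the inconsistency without any power calculation. Severity is minor: the sample size, the 3.0 target, the model and the inference are unaffected.

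**What to change.** Replace the closing sentence of Section 11 with wording such as: *For Exercise + Placebo versus Exercise + Atorvastatin with 36 per arm, a two-sided t-test at unadjusted alpha 0.05 has approximately 80% power for a difference of about 12 µmol/g/min in CS activity and about 2.2 mL/kg/min in VO2peak. Power at a VO2peak difference of 2.0 is about 72% (about 68% with 33 per arm, where 80% power is reached at about 2.3).*

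The change from 2.1 to 2.2 corrects the error. Naming the contrast, n and alpha stops the figure being read as applying to all 120 participants. The added sentence gives the power at the difference the plan itself calls relevant.

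The cost is one figure and one sentence, and a slightly less favourable statement. No participants are added and no analysis changes.
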